## ENGAGES One-Year Outcomes Analysis Plan

Analyses to be completed using R software.

All tests to be 2-sided. P values < 0.05 to be considered suggestive, and P values < 0.005 to be considered as stronger evidence.

### ***Hypothesis 1: Is EEG Guidance Intervention Associated with Reduced One-Year Mortality?***

*Patient Population:* Patients randomized to intervention or control (N = 1232)

*Primary Predictor Variable:* EEG guidance intervention

(X=0 for control or X=1 for intervention)

Intention to treat

*Outcome:* Mortality, with one-year follow up

- Any patient who is lost to follow up before one year will be right-censored at the time of last follow-up. (No assumptions are made about vital status after the date of last follow up.)

*Data Description Plan:* Kaplan-Meier curves, stratified by intervention group

*Analysis Plan:* Cox proportional hazards regression for one-year mortality

- Will perform unadjusted and adjusted analyses
- Will adjust for age, sex, American Society of Anesthesiologists (ASA) physical status classification (1-2 vs 3 vs 4-5), number of comorbid conditions, baseline poor functional capacity (<4 METS), history of falls (yes/no within previous 6 months), evidence of abnormal cognition (preoperative Short Blessed Test score > 4), surgery type (cardiac versus non-cardiac), length of anesthesia (Anesthesia Stop – Anesthesia Start)
  - o Multiple imputation may be used to address missing values of these variables

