##### 2. Worst-Likely-Case Scenario for Missing Data

- o For patients missing baseline quality of life, set the baseline quality of life equal to the mean baseline value for the appropriate stratum of the population. Population to be stratified based on type of surgery (cardiac versus non-cardiac) and history of falls.
- o For patients in the control group missing one-year quality of life, set the quality of life value equal to the maximum postoperative quality of life within the patient's stratum (still stratified by type of surgery and history of falls).

- For patients in the intervention group missing one-year quality of life, set the quality of life value equal to the minimum postoperative quality of life within the patient's stratum (still stratified by type of surgery and history of falls).
- Patients who die before one year will be excluded.

3. Expanded Control Group with Matched Cohort

- Each patient randomized in the ENGAGES trial will be matched to a patient enrolled in the SATISFY-SOS study.
  - All patients enrolled in SATISFY-SOS who meet the following criteria will be considered.
    - Age 60 or older
    - Hospital stay  $\geq$  2 days
    - Surgery between January 2015 and May 2018 (same dates as ENGAGES)
  - For each patient meeting the above criteria, a propensity score for enrollment in the ENGAGES trial will be constructed using logistic regression. Covariates included in the model will include age, sex, ASA physical status, surgery type (cardiac versus non-cardiac), and history of falls.
  - (Because all patients enrolled in ENGAGES were co-enrolled in SATISFY-SOS, the population described above will include all patients who were enrolled in ENGAGES.)
  - Patients enrolled in ENGAGES will be matched 1:1 without replacement to SATISFY-SOS patients not enrolled in ENGAGES based on the logit of the propensity score. A greedy nearest-neighbor algorithm will be used, with a maximum caliper width of  $0.2 * \text{the standard deviation in the logit of the propensity score}$ .
  - Use the same model structure described above.
  - Add a variable to Z indicating whether the patient was enrolled in ENGAGES.

4. Patient-Reported Subjective Quality of Life Change

- Analysis to include the subset of patients enrolled in ENGAGES who returned the SATISFY-SOS survey at one year
  - The survey includes a question asking if quality of life is better, the same, or worse compared to before surgery

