***Hypothesis 3: Is EEG Guidance Intervention Associated with Fewer Falls One Year After Surgery?***

*Patient Population:* Patients randomized to intervention or control (N = 1232)

*Primary Predictor Variable:* EEG guidance intervention

(X=0 for control or X=1 for intervention)

Intention to treat

*Outcomes:* Presence or absence of fall(s) during the one-year postoperative follow-up period, measured via patient report one the one-year ENGAGES survey

- Patients who did not fill out the survey (including both living non-respondents and deceased patients) will be excluded

*Data Description Plan:* Confusion matrix of falls versus EEG guidance intervention

*Analysis Plan:* Logistic regression

- Will perform unadjusted and adjusted analyses
- Will adjust for age, sex, American Society of Anesthesiologists (ASA) physical status classification (1-3 vs 4-5), number of comorbid conditions, history of falls (yes/no within previous 6 months), evidence of abnormal cognition (preoperative Short Blessed Test score > 4), surgery type (cardiac versus non-cardiac), length of anesthesia (Anesthesia Stop – Anesthesia Start)
  - o Note that ASA is dichotomized in this analysis, and functional capacity <4 METS has been dropped. These changes were made to reduce the number of degrees of freedom in the model, with the goal of having one degree of freedom per 10 patients who fell.
  - o Multiple imputation may be used to address missing values of these variables

*Planned Sensitivity Analyses*

1. Deceased Patients
  - o Assume all patients who die within one year have fallen.
2. Best-Case Scenario for Missing Data
  - o Assume all patients who die within one year have fallen.
  - o Assume that living patients in the intervention group with missing fall outcome data have not fallen. Assume that living patients in the control group with missing fall outcome data have fallen.
3. Worst-Case Scenario for Missing Data
  - a. Assume all patients who die within one year have fallen.
  - b. Assume that living patients in the intervention group with missing fall outcome data have fallen. Assume that living patients in the control group with missing fall outcome data have not fallen.
4. Expanded Control Group with Matched Cohort
  - o Use the same matched cohort as described above in Hypothesis 2.
  - o Perform a logistic regression as described above, also adjusting for whether the patient was enrolled in ENGAGES.
5. Number of Falls

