  - o For patients who completed the SATSIFY-SOS 1-year survey, we have a categorical variable detailing the number of falls (0, 1, 2, or 3+).
  - o Perform an ordinal logistic regression, adjusting for the variables described above.

*Exploratory Analyses:*

1. Is duration of intraoperative EEG suppression (minutes with suppression ratio > 1%) associated with mortality?
  - a. Cox proportional hazards model, adjusting for same variables as in hypothesis #1
  - b. Instrumental variable analysis will be used to account for the EEG intervention

2. Is duration of intraoperative EEG suppression (minutes with suppression ratio > 1%) associated with worse quality of life at one year?
  - a. Generalized linear model, same structure as in hypothesis #2
  - b. Instrumental variable analysis will be used to account for the EEG intervention
3. Is duration of intraoperative EEG suppression (minutes with suppression ratio > 1%) associated with more falls at one year?
  - a. Logistic regression, adjusting for same variables as in hypothesis #3
  - b. Instrumental variable analysis will be used to account for the EEG intervention
4. Is duration of intraoperative BIS < 40 associated with mortality?
  - a. Cox proportional hazards model, adjusting for same variables as in hypothesis #1
  - b. Instrumental variable analysis will be used to account for the EEG intervention
5. Is duration of intraoperative BIS < 40 associated with worse quality of life at one year?
  - a. Generalized linear model, same structure as in hypothesis #2
  - b. Instrumental variable analysis will be used to account for the EEG intervention
6. Is duration of intraoperative BIS < 40 associated with more falls at one year?
  - a. Logistic regression, adjusting for same variables as in hypothesis #3
  - b. Instrumental variable analysis will be used to account for the EEG intervention
7. Is median intraoperative end-tidal anesthetic concentration value (measured in MAC) associated with mortality?
  - a. Cox proportional hazards model, adjusting for same variables as in hypothesis #1
  - b. Instrumental variable analysis will be used to account for the EEG intervention
8. Is median intraoperative end-tidal anesthetic concentration value (measured in MAC) associated with worse quality of life at one year?
  - a. Generalized linear model, same structure as in hypothesis #2
  - b. Instrumental variable analysis will be used to account for the EEG intervention

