METHODS AND ANALYSIS: This is a 1,232 patient, block-randomized, double-blinded, comparative effectiveness trial. Patients older than sixty, undergoing volatile agent-based general anesthesia for major surgery, are eligible. Subjects are randomized to one of two anesthetic approaches. One group receives general anesthesia with clinicians blinded to EEG monitoring. The other group receives EEG-guidance of anesthetic agent administration. The outcomes of postoperative delirium (≤ 5 days), falls (≤ 1 month) and health-

between groups will be presented with 95% confidence intervals, and will be considered statistically significant at a two-sided $p<0.05$.

ETHICS AND DISSEMINATION: ENGAGES is approved by the ethics board at Washington University.

Recruitment began in January 2015. Dissemination plans include presentations at scientific conferences, scientific publications, internet-based educational materials, and mass media.

REGISTRATION DETAILS: ENGAGES is registered on clinicaltrials.gov, NCT02241655 (updated February 2015).

Strengths

- The ENGAGES study is a pragmatic clinical trial, conducted in a real world clinical setting.
- The study will enroll older patients, who are under-studied in clinical research.
- The primary outcome, postoperative delirium, is important to patients, healthcare providers and society.
- The electroencephalography-guided anesthetic protocol is straightforward and inexpensive; it would be feasible to disseminate and implement broadly.
- The study utilizes reliable and granular data from the perioperative electronic medical record and incorporates data from a large registry of postoperative patient reported outcomes.

Limitations

- A single clinical trial should seldom be regarded as definitive; if the results of this trial do suggest that EEG-guidance of anesthesia decreases postoperative delirium, it will be necessary to replicate this finding in future studies.
- While patients and those assessing the primary outcome are blinded, the inability to blind clinicians to the trial allocation group is a potential source of bias and confounding.
- The effectiveness of the electroencephalography-guided anesthetic protocol will depend on clinicians' adherence to the protocol.
- As delirium is a fluctuating disorder, it may occasionally be missed despite rigorous and validated assessment methods.

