Randomization will be performed at the patient level using computer-generated assignment. Eligible patients who provided written informed consent will be randomized to receive the intraoperative electroencephalography-guided protocol or routine care. In order to ensure that there is not major imbalance between group assignments with respect to history of falls and cardiac surgery, subjects will be randomized (1:1) between the EEG-guided and routine care groups in blocks of 20 within these four strata (i.e., cardiac surgery with a history of falls within 6 months, cardiac surgery without a history of falls within 6 months, non-cardiac surgery with a history of falls within 6 months; and non-cardiac surgery without a history of falls within 6 months). Trained members of the research team will enroll participants and will implement the assignment of participants to the EEG-guided or usual care protocols. Group assignment will be revealed to members of the anesthetic team only when the patient enters the operating room by opening a sequentially numbered, opaque, sealed envelope in a sequence generated by one of the study's data analysts. Patients and their families will be blinded to group allocation and different members of the research team will assist with the intervention in the operating room (will not be blinded to the intervention) from those conducting the postoperative assessments (will be blinded to the intervention).^{51,52} To reduce predictability of a random sequence, details of patients already randomized and prior group assignments will be recorded in a separate document that is unavailable to those who enroll participants and assign interventions.

Primary Intervention – EEG-guided Anesthetic Protocol

The primary intervention to which patients will be randomized in this study is a pragmatic EEG-guided anesthetic protocol (See Appendix). All anesthesia practitioners will receive a targeted educational session on recognition of EEG patterns typically occurring during general anesthesia. The content will be similar to that described in an article where we demonstrated that anesthesiologists could estimate BIS (processed EEG

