We will follow the intention-to-treat principle for all analyses. The primary endpoint of our analysis is the incidence of postoperative delirium as defined previously. The incidence of delirium will be compared between groups using a chi-square test, and the difference in delirium incidence with 95% confidence intervals will be calculated. Prespecified exploratory subgroup analyses: we will test for effect modification by known baseline delirium risk factors (i.e., age [<70 and ≥ 70], sex, history of falls, and type of surgery [cardiac versus non-cardiac]).

ii) Effectiveness of EEG-guided anesthesia protocol in improving patient reported outcomes of health-related quality of life and preventing postoperative falls (Aim 2 in Figure 2)

Health-related quality of life

Random effects regression models based on PROC MIXED in SAS will be used to compare Physical Summary Score change over 12 months between the intervention and usual care group by introducing terms for time, indicator variables for treatment group and time x treatment group interactions with the latter set of regression coefficients of primary interest. The model will be controlled for baseline health-related quality of life. Potential confounding factors including age, gender and relevant comorbidities will be evaluated and controlled for in the model. We will utilize the same analysis approach to evaluate the Mental Summary Scores.

The analysis is primarily based on the following model: $Y_{it} = \alpha + \beta_1 t + \beta_{2A} X_{i1} + \beta_{3A} X_{i1}t + \beta_4 Y_{i0} + e_{it}$ (1) where Y_{it} = QOL for subject i at time t , where $t = 0$ for baseline, $t = 1$ for 12 months. $X_{i1} = 1$ if i th subject is in the Intervention group, = 0 otherwise $e_{it} \sim N(0, \sigma^2)$ β_{3A} is the mean difference in Physical Summary Score change between the Intervention and usual care groups. The coefficient β_{2A} allows for mean differences in Physical Summary Scores between groups at baseline. The coefficient β_4 allows the change in Physical Summary Score to depend on initial level.

Postoperative falls

Chi square test will be used to compare the incidence of falls at 12-months postoperatively between patients in the EEG-guided and in the usual care groups.

iii) Explore whether a multi-component safety intervention is associated with improved patient reported health-related quality of life and decreased incidence of postoperative falls (Aim 3 in Figure 2)

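### The adjusted models for mortality, quality of life and falls condition on length of anesthesia, which is completed after allocation by clinicians who know the arm

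*SAP*

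**What the plan says.** The covariate "length of anesthesia (Anesthesia Stop – Anesthesia Start" appears in the Analysis Plan of SAP Hypotheses 1 (Cox model), 2 (linear predictor for the VR-12 scores) and 3 (logistic model for falls). All three are labelled intention to treat, with assignment as the primary predictor. Each plans an unadjusted and an adjusted analysis, and neither is named primary.

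The list also carries into other analyses:

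- The Hypothesis 2 matched-cohort sensitivity analysis says "Use the same model structure described above", and the Hypothesis 3 version likewise reuses the main logistic model.
- The number-of-falls analysis says "Perform an ordinal logistic regression, adjusting for the variables described above".
- Exploratory Analyses 1 to 9 reuse the covariates or model structure of Hypotheses 1 to 3, for example "Cox proportional hazards model, adjusting for same variables as in hypothesis #1".

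On timing, the protocol's Randomization and Blinding section states: "Group assignment will be revealed to members of the anesthetic team only when the patient enters the operating room". Its Limitations list adds that "the inability to blind clinicians to the trial allocation group is a potential source of bias and confounding".

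The protocol's own plan for quality of life (Statistical Analyses) says: "Potential confounding factors including age, gender and relevant comorbidities will be evaluated and controlled for in the model". Its falls comparison is an unadjusted chi-square test. Neither mentions duration.

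**The concern.** Covariate adjustment in a randomised comparison keeps the meaning of the treatment effect when the covariates are fixed before allocation. Every other listed covariate is a preoperative characteristic or surgery type, which is a stratification factor. Length of anesthesia is different. The SAP does not define the event that starts the clock, but the stop time necessarily falls after the arm is known, and the intervention acts during the interval being measured.

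If assignment shifts duration, two things happen to the adjusted coefficient. It no longer contains any effect that runs through duration, so it answers a different question from the intention-to-treat one. It also becomes open to bias: among patients with the same duration, the arms would differ in unmeasured surgical complexity, which drives both duration and outcome. The models' only descriptor of the procedure is cardiac versus non-cardiac, so much complexity is left unmeasured.

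At stake is the reading of the adjusted results. If they differ from the unadjusted ones, the reader cannot tell a gain in precision from a change in what is estimated. The SAP gives no rationale for the covariate, no comparison of duration by arm and no adjusted model without it.

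**Working it through.** The plan gives no figure to reproduce here. The documents give neither the effect of EEG guidance on duration nor the prognostic strength of duration, so both are assumed and the aim is only to show the scale.

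**Inputs for mortality.** From the SAP: 1,232 patients. The protocol gives 616 per arm. Assumed: one-year mortality 10%; b = 0.2 log-hazard per hour of anesthesia; unmeasured complexity U (SD 1) adding a = 0.8 h to duration and g = 0.5 to the log-hazard; residual SD of duration s = 0.5 to 2 h; EEG arm shorter by 0, 5, 10 or 20 minutes.

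**Closed form.** Let duration = −d·arm + a·U + noise, where d is the shortening in hours.

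- Total effect through duration: −b·d, which the adjusted model removes.
- Path opened by conditioning on duration: +d·a·g/(a² + s²).
- Adjusted minus total log-HR: d × [b + a·g/(a² + s²)].

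For 10 minutes (d = 1/6), with a·g = 0.4 and a² = 0.64:

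- s = 0.5: (0.2 + 0.4/0.89)/6 = 0.108
- s = 1.25: (0.2 + 0.4/2.2025)/6 = 0.064
- s = 2: (0.2 + 0.4/4.64)/6 = 0.048

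**Standard error.** 10% of 1,232 is about 123 deaths, and 2/√123 ≈ 0.18.

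**Cox simulation** (616 per arm, censoring at one year, 1,500 replicates), adjusted minus unadjusted log-HR:

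| Shortening in EEG arm | Closed form (s = 0.5 / 1.25 / 2 h) | Simulation, range over s | Divided by 0.18 |
|---|---|---|---|
| none | 0 | 0.000 to 0.001 | about 0 |
| 5 min | 0.054 / 0.032 / 0.024 | 0.024 to 0.055 | 0.1 to 0.3 |
| 10 min | 0.108 / 0.064 / 0.048 | 0.045 to 0.108 | 0.25 to 0.6 |
| 20 min | 0.216 / 0.127 / 0.095 | 0.093 to 0.214 | 0.5 to 1.2 |

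A lengthening would act in the opposite direction. At s = 1.25 h the 10- and 20-minute gaps were 0.064 and 0.128 with 5% mortality (SE 0.26), and 0.062 and 0.123 with 15% (SE 0.15). With a direct log-HR of −0.35 the gaps for 5, 10 and 20 minutes were 0.026, 0.058 and 0.121, so they do not depend on assuming no direct effect.

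**Power.** With a direct HR of 0.70 and s = 1.25 h, adjusted versus unadjusted power was 38% vs 43% (5 min), 36% vs 48% (10 min) and 31% vs 54% (20 min).

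**Quality of life.** A linear model used standardised duration, with slopes of −0.2 for duration and −0.5 for complexity, together and one at a time. Results are scaled by the protocol's SD of 2.5. The bias was about zero with no shift, −0.05 to −0.12 points for a shift of −0.1 SD, and −0.10 to −0.23 points for −0.2 SD. The last range is 20% to 45% of the protocol's 0.5-point difference (0.10/0.5 and about 0.227/0.5).

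**Falls.** With the protocol's 40% rate as baseline, a true OR of 1 and only the complexity path active, the adjusted OR was 1.00, 1.03 and 1.06 for shifts of 0, −0.1 and −0.2 SD.

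**The case against.** The strongest reply is that nothing in the documents says EEG guidance changes duration. The protocol expects less anesthetic and less EEG suppression. Its section on premature termination discusses awareness, movement, blood pressure and heart rate, not case length. This stands, and it is why the conclusion is conditional.

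Second, unadjusted analyses are planned for all three outcomes and are unaffected. This also stands, but it does not make the adjusted results interpretable, and the SAP leaves open which will lead.

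Third, the size depends on assumed slopes. Halving b, a and g at s = 1.25 h gives (0.1 + 0.1/1.7225)/6 = 0.026 for 10 minutes, about 0.15 SE. The upper end of 1.2 SE needs a 20-minute shift with s = 0.5 h, where complexity explains 0.64/0.89 = 72% of duration variance. The other SAP covariates might absorb some complexity. About half of the gap at s = 1.25 h (0.2/0.382 = 52%) is a changed estimand rather than bias, and the widening power contrast partly reflects the benefit that each larger shift adds to the unadjusted effect. All of this is fair, and it supports calling the effect mostly modest.

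Fourth, in the matched-cohort models the contrast of enrolled with non-enrolled patients is not randomised, and dropping duration removes its only marker of case length. But the target there is the EEG coefficient, which the enrollment indicator protects.

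Finally, the protocol's quality-of-life covariate list is open-ended, so the absence of duration from it is supporting evidence only.

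**Conclusion.** The concern holds as a conditional one. Length of anesthesia is a post-allocation variable in every adjusted model of the randomised comparison, and it is the only listed covariate that assignment could affect. With no arm effect on duration the distortion is about zero. With shifts of 5 to 20 minutes it is roughly 0.1 to 1.2 standard errors of the mortality log-HR under the assumed inputs, mostly in the lower part of that range. The figures for quality of life and falls are illustrative only. Size and direction cannot be derived from the documents. The point is worth fixing because the adjusted results now rest on an untested assumption that assignment leaves duration unchanged, and removing that dependence is cheap.

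**What to change.** Delete length of anesthesia from the covariate lists of Hypotheses 1 to 3. The deletion then carries by reference into the matched-cohort and number-of-falls sensitivity analyses, so that these models use only variables fixed before allocation. Report length of anesthesia by arm. If a duration-adjusted result is wanted, keep it as a labelled sensitivity analysis. A planned case length or finer procedure category could take its place, provided it was recorded before allocation.

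Give Exploratory Analyses 1 to 9 their own covariate list if actual length is to stay in the non-randomised exposure models (part a). State the covariates for the instrumental-variable analyses (part b), and leave length out there if assignment is the instrument.

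The cost is three edited lists and one new one. Some precision is lost if duration is prognostic: in simulation with no arm shift and HR 0.70, power was 40.8% without the covariate versus 41.7% with it at 0.2 log-hazard per hour, and 37.2% versus 40.4% at 0.3. In Hypothesis 3 the model goes from 9 to 8 degrees of freedom counting treatment, which fits the SAP's stated aim there: "with the goal of having one degree of freedom per 10 patients who fell". Naming the primary version is a separate decision. With this change, both versions estimate an effect of assignment.
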